6.2.4.2. Delivery Device Weights

The weight of each IP-filled device will be collected prior to dose administration and the weight recorded in the eCRF at the time point specified in the Schedule of Events (Table 3). Following administration of the dose (active and placebo) the actuated device will again be weighed, and the weight recorded in the eCRF. A calculation of the filled device weight minus the emptied device weight will indicate the weight of dose that was delivered from the device and will be used to determine volume dispensed.

6.2.4.3. Blood Collection for Influenza Antibody Testing

Blood samples will be collected and used for serum antibody titers against influenza using microneutralization (MN) and research assays. Samples will be collected as indicated in the Schedule of Events (Table 3).

The MNT will measure all serum antibodies that neutralize the virus and prevent infection of cells and will be analyzed as directed in the Laboratory Manual.

Research testing will be performed by the Sponsor or a vendor under supervision of the Sponsor. The research assays include enzyme-linked immunosorbent assays (ELISAs) or similar methods that may be used to detect anti-influenza immunoglobulin G (IgG) and/or IgA antibodies against influenza HA, HA stalk or NA. Additional assays may be conducted for detection of antibody response to influenza or other respiratory virus, for example neuraminidase inhibition assays (NAI).

Further details regarding sample collection, processing and shipping can be found in the Laboratory Manual.

6.2.4.4. PBMCs for Cell-mediated Immunity Testing

Blood samples will be collected from all subjects at select sites and peripheral blood mononuclear cells (PBMCs) will be isolated and cryopreserved to be tested for CMI. Samples are taken as indicated in the Schedule of Events (Table 3) for ~160 subjects.

PBMCs will be used to evaluate T cell responses by ELISPOT assays measuring cytokine secretion upon stimulation with influenza specific peptides. PBMCs may also be evaluated using flow cytometric (FACS) methods and intracellular cytokine staining (ICS) to characterize the duration of the responses, and whether memory phenotypes are generated. PBMCs may also be used in a direct ex-vivo ELISPOT assay for evaluation of plasma B cell responses or for detection of memory B cell responses after stimulation.

Further details regarding sample collection, processing and shipping can be found in the Laboratory Manual. PBMC preparation will be the responsibility of each site.

6.2.4.5. Plasma for Gene Expression and Cytokine Testing

The plasma fraction will be collected from all subjects at select sites from blood samples processed for PBMC isolation. The plasma will be isolated, at select sites, and cryopreserved for later use for innate transcriptome gene expression and cytokine profile analysis. Samples are taken as indicated in the Schedule of Events (Table 3). These exploratory samples are being collected for research purposes only.

Further details regarding sample collection, processing and shipping can be found in the Laboratory Manual.

Serum, plasma, PBMC and nasal swab samples that remain after protocol-specific assessments have been performed may be used for further exploratory work on pharmacokinetics, metabolites, plasma protein binding, protein analysis, and biochemistry. No human deoxyribonucleic acid (DNA) or ribonucleic acid (RNA) analysis will be performed, except cytokine expression as specified in the protocol or study manual.

7. STUDY TERMINATION/COMPLETION

7.1. Study Completion and End of Study Definition

A subject will be considered to have completed the study if he or she received the last study vaccination and attended the last protocol-defined follow-up visit.

End of study will be defined as the point when all patients have completed follow up. The Sponsor will notify all applicable regulatory agencies in accordance with local requirements when the study has ended.

7.2. Termination of the Study by the Sponsor

This study may be discontinued at any time due to safety concerns, failure to meet expected enrollment goals, administrative reasons, or at the discretion of the Sponsor. Should the study be terminated prematurely, the Sponsor will provide written notification to all Investigators and regulatory authorities and will specify the reason(s) for early termination. The Lead PI must inform the IRB promptly and provide the reason(s) for the termination.

7.3. Study Halting Rules

Vaccination of subjects will be suspended until after review of safety data by the SRC if any of the following halting rules are met:

1. One or more subjects experience a Grade 4 AE, vital sign or laboratory AE that cannot be clearly attributed to another cause.
2. Three or more subjects within a single sentinel group or ten or more subjects within the expansion group experience the same Grade 3 AE, vital sign or laboratory AE that cannot be clearly attributed to another cause.
3. One or more subjects experiences a SAE assessed as related to IP.
4. One or more subjects has laryngospasm, bronchospasm, or anaphylaxis associated with the study product within 72 hours of product administration.

Any AE or SAE that falls into the above criteria for suspending or terminating the study (including the occurrence of **any** Grade 3 AE, vital sign or laboratory AE that cannot be clearly attributed to another cause) must be reported by the investigator to the Sponsor **immediately (within 24 hours)**.

In the case of halting rules being met, the SRC will be convened as quickly as possible. After review of the safety data the SRC will make a recommendation to the Sponsor whether to resume, suspend or terminate the study. The Sponsor will communicate a decision to suspend or terminate the study to the Investigators.

Subsequent review of serious, unexpected, and related AEs by the Medical Monitor, SRC, IRB, the Sponsor(s), or the FDA or relevant local regulatory authorities may also result in suspension of further trial interventions/administration of study product at a site. The FDA and study Sponsor(s) retain the authority to suspend additional enrollment and study interventions/administration of study product for the entire study, as applicable.

7.4. Removal of Subjects from the Study

Subjects have the right to withdraw from the study at any time for any reason, including personal reasons. A subject can withdraw without giving a reason. The Investigator should however try to determine why a subject withdraws from the study and document the reason for withdrawal in the source documents and in the EDC system.

Subjects **may** be withdrawn from the study in the event of:

- Meeting any of the halting rules in [Section 7.3](#)
- A severe AE or serious AE (SAE);
- Difficulties in obtaining blood or other samples;
- Failure of the subject to comply with the protocol requirements or to cooperate with the Investigator.

Subjects **must** be withdrawn from the study in the event of:

- Withdrawal of consent
- Lost to follow-up
- Death
- Termination of the study by the Sponsor (described in [Section 7.2](#))
- For safety reasons, it being in the best interest of the subject that he/she be withdrawn, in the Investigator’s opinion;
- A positive pregnancy test (the subject or, if reported by a male subject, his female partner), or if the subject/partner is non-compliant with the contraception requirements (see [Section 4.1](#));
- Development of a medical condition that requires concomitant treatment with a prohibited therapy (see [Section 5.9.2](#));
- Breaking of the randomization code during administration of the study drugs. If the code is broken for safety reporting purposes, the subject may remain in the study; however, in such case subject and site staff will remain blinded to IP treatment.

The monitor and Sponsor will be informed in the event of a subject being withdrawn from the study. In case of withdrawal due to an SAE (for details on AE reporting see [Section 9.7](#)), the Sponsor should be notified within 24 hours; in case of withdrawal for other reasons; the Sponsor should be notified within 2 days from the event.

Subjects who are withdrawn from the study prior to completion of the scheduled study procedures for any reason (AE, withdrawal of consent, etc.) should be invited to complete the assessments as much as possible: as long as the subject consents, all relevant assessments of the day on which the subject withdrew from the study should be completed, at least those related to safety, and the subject should come for a safety follow-up visit 4 weeks after vaccination. In case of an AE, the appropriate follow-up will be done.

Subjects who are withdrawn from the study will not be replaced.

8. STATISTICAL METHODS AND CONSIDERATIONS

8.1. General Considerations

Prior to the analysis of the study data, statistical methods and table shells will be detailed in a Statistical Analysis Plan (SAP) and finalized before database lock.

The final analysis will be done after the last subject has had the day 57 visit and the data base has been locked. The day 209 data will be included as a supplemental analysis.

Statistical analysis will be the responsibility of Northrim Consulting, Inc, using SAS® (SAS Institute Inc., Cary, NC, USA; version 9.4 or higher).

There are primary, secondary and exploratory objectives, endpoints and analyses. Depending upon the result of the primary and secondary analyses, not all exploratory analyses may be done.

Safety and subject disposition analyses will be conducted on the safety analysis set.

Summarization of primary and secondary efficacy endpoints will be done using FAS. These summaries may be repeated using the PP analysis set.

There are no formal tests of hypotheses in this study. Efficacy outcomes are descriptive only.

The data will be summarized in tables listing the number, mean, standard deviation, median, minimum, maximum, standard error (SE) and a 95% CI of subjects for continuous data, or in tables listing count and percentage for categorical data where appropriate. Tables will be presented by IP treatment and overall. Data listing by subject will be provided.

8.2. Analysis Sets

The following populations are defined for this study:

- Safety Set (SS) – consists of any subject who receives at least one administration of IP;
- Full Analysis Set (FAS) – consists of all subjects randomized, received IP and had at least one post baseline assessment.
- (If necessary) Per-protocol Set (PP) - consists of all subjects in FAS with no major protocol violations or deviations.

Unless otherwise specified the FAS population will be used for analysis.

8.3. Subject Disposition and Baseline Comparability

Subject disposition will be tabulated; the number of enrolled, randomized, prematurely terminated and completed subjects will be summarized by IP treatment group and overall. A list of dropouts will be prepared including reason and (study) time of discontinuation.

Subject IP treatment groups will be characterized using tables, figures and descriptive statistics for demographic and baseline variables. Observed differences between the groups, should there be any, will be interpreted for clinical significance and their potential use as covariates in the analysis of efficacy endpoints

8.3.1. Sample Size

The sample size of 50 subjects per group was chosen based on reports of studies of other vaccines in early stage development. This study is not powered for any formal comparisons.

8.3.2. Subject Characteristics Data Set

Demographics will include by-treatment summaries of age, height, weight, BMI, race, and gender. BMI will be calculated in metric units using the formula provided below:

$$\text{BMI} = \text{weight (kg)}/\text{height (m)}^2$$

Other baseline characteristics may be summarized.

8.3.3. Safety Analyses

Safety and tolerability of the Bris10 M2SR and Sing2016 M2SR influenza vaccines as assessed by subject diaries, solicited and unsolicited AEs, vaccine -associated AEs, SAEs, safety labs, vital signs, and physical examinations.

Exposure

Vaccine exposure will be summarized by actual dose, % of expected dose, and % of subjects receiving the expected dose.

Adverse Events

Treatment-emergent AEs (local and systemic) will be summarized as N (%) with AEs, with related-AEs, and by worst severity.

Incidence of TEAEs will be reported by MedDRA-coded SOC, PT and maximum severity.

Incidence of most frequent TEAEs and most frequent treatment-related TEAEs will be reported by SOC and PT

Listings of subjects who died, discontinued the study due to an AE, or experienced an SAE will be provided.

Dose-site reactions will be presented by reaction and severity.

Post-administration of symptoms (memory aid) will be summarized by time point, worst occurrence, and days with symptoms.

Clinical Laboratory Tests

Biochemistry and hematology laboratory results and change from baseline results will be summarized by timepoint using descriptive statistics.

Shift tables of maximum grade compared to baseline tabulated according to the FDA guidance: Toxicity Grading Scale for Healthy Adult and Adolescent Volunteers Enrolled in Preventive Vaccine Clinical Trials, or in accordance with the normal ranges of the clinical laboratory (below, within, or above normal range) for parameters for which no toxicity grades are defined.

A listing of clinical laboratory test results outside the reference ranges will be provided.

Vital Signs

Vital sign results and change from baseline results will be summarized by timepoint using descriptive statistics.

Limited Physical Examination

Abnormal findings in physical examination will be listed.

Pregnancy

A listing of pregnant subjects will be displayed.

8.3.4. Additional Analyses

Additional analyses will be descriptive only; p-values are descriptive and not corrected for multiple testing.

Immunogenicity

Serum antibody, mucosal antibody and cellular immune response will be summarized using descriptive statistics by sampling timepoint for all subjects and by baseline values.

Seroconversion rates will be presented by timepoint and by baseline starting values.

Viral shedding will be summarized using descriptive statistics.

Additional (exploratory) endpoints may be analyzed.

8.4. Appropriateness of Measurements

The assessments which will be made in this study are standard, and are generally recognized as reliable, accurate, and relevant.

9. ADVERSE EVENT REPORTING

9.1. Definitions

Adverse Event

An AE is any untoward medical occurrence in a clinical study subject administered a medicinal (investigational or non-investigational) product. An AE does not necessarily have a causal relationship with the treatment. An AE can therefore be any unfavorable and unintended sign (including an abnormal finding), symptom, or disease temporally associated with the use of a medicinal (investigational or non-investigational) product, whether or not related to that medicinal (investigational or non-investigational) product.

This includes any occurrence that is new in onset or aggravated in severity or frequency from the baseline condition, or abnormal result of diagnostic procedures, including clinical laboratory test abnormalities.

AEs will be monitored continuously from the first administration of IP treatment until Day 57. SAEs or medically attended events will be documented until Day 209. Events recorded at the follow-up phone call will be assessed and followed up as appropriate.

Serious Adverse Event

An SAE is any untoward medical occurrence that meets any of the following conditions:

- results in death;
- is life-threatening, i.e., the subject was at risk of death at the time of the event (e.g., ventricular fibrillation and anaphylaxis). The term does not refer to an event which hypothetically might have caused death if it were more severe.
- requires inpatient hospitalization or prolongation of existing inpatient hospitalization:
 - Hospitalization refers to an overnight admission into hospital for the purpose of investigating and/or treating the AE. Hospitalization for an elective procedure, or routinely scheduled treatment for a pre-existing condition that has not worsened, is not an SAE.
- results in persistent or significant disability/incapacity, i.e., causing substantial disruption of the subject's ability to conduct normal life;
- is a congenital anomaly/birth defect;
- is medically significant, i.e., may not be immediately life-threatening or result in death or hospitalization but may jeopardize the subject's health or may require intervention to prevent one of the above outcomes. Examples of such events are intensive treatment in an emergency room or at home for allergic bronchospasm, blood dyscrasias, or convulsions that do not result in hospitalization or development of drug dependency or drug abuse.

Unlisted (Unexpected) Adverse Event

An AE is considered unlisted if the nature or severity is not consistent with the applicable product reference safety information (FluGen IB).

Suspected Unexpected Serious Adverse Reactions (SUSARs)

A SUSAR is an unexpected serious adverse reaction to the IP.

The Sponsor is to determine if the event is unexpected or not and if unexpected and to report the SUSAR to the Lead PI and FDA. The Lead PI will report any SUSAR(s) to the central IRB. For death and life-threatening cases, reporting should be done within 7 days and follow-up information with details provided within an additional 8 days. All other SUSARs have to be reported within 15 days.

9.2. Intensity of Adverse Events

All AEs will be assessed by the clinician using the grading system from FDA vaccine toxicity criteria ([Appendix 1](#) for vital signs and systemic AE assessment; [Appendix 2](#) for laboratory AE assessment, and as described in Section 6.2.2). For assessment of reactogenicity in this study, see [Appendix 3](#). For events not included in the protocol-defined grading system, then the following guidelines will be used to quantify intensity.

Mild: events require minimal or no treatment and do not interfere with the patient's daily activities.

Moderate: events result in a low level of inconvenience or concern with the therapeutic measures. Moderate events may cause some interference with functioning.

Severe: events interrupt a patient's usual daily activity and may require systemic drug therapy or other treatment. Severe events are usually incapacitating.

Life threatening: any adverse drug experience that places the patient or subject, in the view of the investigator, at immediate risk of death from the reaction as it occurred, i.e., it does not include a reaction that had it occurred in a more severe form, might have caused death.

Changes in the severity of an AE should be documented to allow an assessment of the duration of the event at each level of intensity to be performed. Adverse events characterized as intermittent require documentation of onset and duration of each episode.

9.3. Causality Assessment

The clinician's assessment of an AE's relationship to test article (vaccine or placebo) is part of the documentation process, but it is not a factor in determining what is or is not reported in the study. If there is any doubt as to whether a clinical observation is an AE, the event should be reported. All AEs must have their relationship to study product assessed using the terms related or not related. In a clinical trial, the study product must always be suspect. To help assess, the following guidelines are used.

Related – There is a reasonable possibility that the study product caused the AE. Reasonable possibility means that there is evidence to suggest a causal relationship between the study product and the AE.

Not Related – The AE is not related to the study product if there is evidence that clearly indicates an alternative explanation. If the subject has not received the study product, the timing of the exposure to the study product and the onset of the AE are not reasonably related in time, or other facts, evidence or arguments exist that strongly suggest an alternative explanation, then the AE is not related.

9.4. Reactogenicity

Reactogenicity events may be common and are known to occur for the vaccine being studied and will be collected as solicited AEs in a standard, systematic format using a grading scale based on functional assessment or magnitude of reaction. In this study, the following reactogenicity events will be collected for the first 7 days after each dose of IP:

- Feverish
- Nasal irritation
- Nasal bleeding
- Runny nose
- Stuffy nose/Congestion
- Sore/scratchy/itchy or painful throat
- Body/muscle aches
- Joint pain
- Headache
- Cough
- Body rash
- Tiredness
- Nausea
- Vomiting
- Other symptoms

These will be evaluated and graded daily based on the functional scale specified within the Symptom Memory Aid ([Appendix 5](#)).

Should a subject experience a severe reaction (graded as a 3) and/or measure a body temperature equal to or greater than 39°C, he/she should immediately contact the site.

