2	Moderate - events may cause some interference with daily activities
3	Severe - events may require medication or other treatment. Severe events usually prevent daily activities.

	Study Day Date (dd/mmm/2019)	Day 1 (Dosing Day) ___/___/2019	Day 2 ___/___/2019	Day 3 ___/___/2019	Day 4 ___/___/2019	Day 5 ___/___/2019	Day 6 ___/___/2019	Day 7 ___/___/2019
Other Symptoms (Describe)								
Include Intensity Level (0-3)								

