9.2.1. Reactogenicity Assessments: Symptom Memory Aide (SMA)

Fourteen (14) different reactogenicity symptoms (including other/specify) are collected pre-IP administration and once daily for the 7 days following each of the IP administrations via a "Symptom Memory Aide (SMA)", see Protocol Appendix 5. Symptoms are reported by the subject, at 4 levels of intensity (0=None, 1=Mild, 2=Moderate, 3=Severe).

Each symptom will be summarized by severity (worst reported over the course of the 7 days) by treatment and whether subjects experienced a given symptom at any severity. This summary will be done for IP administration 1 and repeated for IP administration 2. Symptom category "other" will be included in the listings only.

Each symptom will be summarized by the number of days with symptoms for each subject. This summary will be done for IP administration 1 and repeated for IP administration 2. Symptom category "other" will be included in the listings only.

Each symptom (and oral temperature) will be summarized by IP administration (1 or 2) and timepoint (Day 1 pre-dose (coded as Day 0), Day 1 post dose, Days 2-7). Summary statistics will be given for oral temperature (mean, SD, median, min, max) and as yes/no (0,1, missing) for each symptom. Symptom category "other" will be included in the listings only.

These summaries will use the EVAL set.

SMA symptoms will not be grouped into local and/or systemic events.

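### SAP 9.2.1 sends the memory aid's 'other' symptoms to listings only, so unlisted symptoms have no 7-day, per-dose, subject-graded rate by arm

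*Protocol*

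**What the plan says.** Protocol 9.4 says that reactogenicity events "will be collected as solicited AEs in a standard, systematic format using a grading scale based on functional assessment or magnitude of reaction". It then states that "the following reactogenicity events will be collected for the first 7 days after each dose of IP" and lists 14 named symptoms followed by 'Other symptoms'. Of the whole list it says: "These will be evaluated and graded daily based on the functional scale specified within the Symptom Memory Aid". The diary in Protocol Appendix 5 agrees. It has a grid of 14 symptom rows and a separate free-text chart for other symptoms, with an intensity from 0 to 3 for each day.

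Protocol 8.3.3 plans that memory-aid symptoms "will be summarized by time point, worst occurrence, and days with symptoms", with no exception for the last item.

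SAP 9.2.1 opens with "Fourteen (14) different reactogenicity symptoms (including other/specify) are collected pre-IP administration and once daily for the 7 days following" each administration. It then sets out three summaries, each given separately for dose 1 and dose 2: worst severity, number of days with the symptom, and occurrence by time point. After each one it says that the 'other' category "will be included in the listings only".

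There is a second route. Under Protocol 6.2.1.6 and SAP 9.2, staff reviewed diary entries for recording as AEs, and recorded events are tabulated by SOC, PT and maximum severity. SAP 9.2 also says that a diary symptom was not necessarily reported as an AE, and that the diary and AE data were not reconciled. SAP section 12, which records changes to the planned analyses, does not mention the treatment of 'other'.

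**The concern.** The Protocol makes 'Other symptoms' a solicited, graded item, and the SAP then leaves it out of every memory-aid summary. Several complaints that the documents themselves treat as relevant have no named diary row. Protocol 6.2.4.1 asks for an extra swab if diarrhea or conjunctivitis occurs within 7 days of vaccination, and Appendix 1 has a grading row for diarrhea. Protocol 6.1.3 lists chills separately from fever. SAP 9.2 names sneezing, itchy eyes and hoarseness in its upper respiratory grouping. Wheeze and breathlessness have no row either. The free-text chart is the natural diary field for all of these, although some chills may be entered under 'Feverish'.

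Safety and tolerability after one and after two administrations is the primary objective, and Sing2016 M2SR is being given to humans for the first time. A reaction that nobody thought to name is one that a by-dose, by-arm table should be able to show. Under the SAP a reader would have to build that rate by hand from a listing of free text.

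**Working it through.** **Step 1: the count.** Protocol 9.4 (and the same list in 6.2.1.6) has 14 named symptoms + 1 'Other' = 15. Appendix 5 has 14 grid rows + 1 'Other' chart = 15. The SAP's figure is 14 with 'other' included, which would leave 14 − 1 = 13 named symptoms. It is reproduced only if 'other' is left out, which contradicts the SAP's own parenthesis. The SAP is one short.

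**Step 2: what is tabulated.** Of the three memory-aid summaries in SAP 9.2.1, 'other' appears in 0 of 3, for either dose.

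**Step 3: whether the AE tables supply the same quantity.**

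| | Named symptom, memory-aid tables | 'Other' symptom, memory-aid tables | Same symptom, AE tables (SAP 9.2) |
|---|---|---|---|
| Shown by arm | Yes | No row | Yes, if recorded as an AE |
| Window | 7 days after each dose | – | First dose to last dose + 30 days; no upper limit if related |
| Split by dose | Yes | – | Not planned |
| Who grades | Subject, daily | – | Investigator |
| Completeness | All diary entries | Listing only | Investigator's judgement; not reconciled with the diary |

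The AE tables overlap with the missing rows but do not replace them.

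**Step 4: size, for illustration.** The documents give no expected rate for any unlisted symptom, so true rates p of 2%, 5% and 10% are assumed. SAP section 12 puts enrollment at about 40 per arm. The memory-aid tables use the Evaluable Set, so their denominators may be a little smaller. The chance of at least one case in an arm is 1 − (1 − p)^40:

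- p = 2%: 1 − 0.98^40 = 0.554
- p = 5%: 1 − 0.95^40 = 0.871
- p = 10%: 1 − 0.90^40 = 0.985, with 40 × 0.10 = 4 cases expected

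A tabulated row would carry the following (exact 95% limits):

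- 4/40 = 10.0% (2.8 to 23.7)
- 2/40 = 5.0% (0.6 to 16.9)
- 0/40 = 0% (0 to 8.8)

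Even an empty row says something, since 0/40 bounds the rate at 8.8%. With no row, the reader cannot tell none from not tabulated. These probabilities show how likely there is to be something to tabulate. They do not measure a loss of data.

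**The case against.** A reader might infer that the plan leaves unlisted reactions without a rate anywhere, or hides airway reactions. The documents do not support that. The listings-only rule covers the memory-aid summaries alone. SAP 9.2 says investigators were told to record individual diary symptoms as AEs so that reactogenicity would be captured, and Protocol 9.3 says to report in case of doubt. Once recorded, wheeze, chills or diarrhea is coded and tabulated as N (%) by treatment and maximum severity. Airway signs have further routes: lung examination for wheeze after each dose and at follow-up visits, scripted calls on Days 4 and 32, and a listing of halting-rule events by subject and treatment. No data are lost, because the entries stay in the listing.

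The 'other' chart also differs from the grid. It is free text on a generic scale, and its header shows no pre-dose column. One row pooling unlike complaints gives no rate for any one of them. Listing free text and leaving tabulation to coded AEs is a defensible choice, and Protocol 8.1 leaves detail to the SAP.

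Most of this stands, and it limits the point. What it does not answer is that SAP 9.2 itself describes the AE route as discretionary and unreconciled, and that the AE tables are neither split by dose nor confined to 7 days. The pooling argument is a reason to code the entries, not to leave them out. If the AE tables were meant to be the source, the SAP does not say so.

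**Conclusion.** The gap is real but narrow. SAP 9.2.1 departs from the plain reading of Protocol 9.4 and 8.3.3, and unlisted symptoms get no 7-day, per-dose, subject-graded rate by arm. They appear in the AE tables only if the investigator recorded them, and the plan has no check on how often that happened. The practical size depends on how many 'other' entries there are, which the documents do not give. The 87% and 98.5% figures rest on assumed rates of 5% and 10% and about 40 subjects per arm.

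The miscount is a separate, clerical matter. A reader might take it to mean that a named symptom was dropped, or that it causes the missing rows. Neither is supported: 14 matches the fixed rows of the diary grid, and the missing rows come only from the listings-only rule. The point bears on the primary safety objective, is partly mitigated by the AE tables, and is worth correcting because the data are already collected.

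**What to change.** In SAP 9.2.1:

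1. Code each 'other' entry to a MedDRA preferred term.
2. Add to the per-dose memory-aid tables an 'any other symptom' N (%) row by treatment, worst severity and number of days, on the same denominators as the named symptoms.
3. Below it, add a row for each coded term reported by 2 or more subjects. Without these rows the pooled row gives no symptom-specific rate.
4. Flag for each 'other' entry whether a matching AE record exists, so that diary and AE rates for the same term can be read together and not as two conflicting figures.
5. Keep the listing.
6. Correct the count to 14 named symptoms plus 'other', 15 in all.

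If the sponsor prefers not to tabulate, the minimum is to name the SOC/PT tables as the intended source, reconcile the 'other' entries with the AE records, and note the departure from Protocol 8.3.3 in SAP section 12.

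The cost is coding of free-text entries, whose number is not stated, a matching flag and a few sparse rows. No new data are needed.
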